9.5 Clinical Laboratory Measurements

Hematology

Complete blood count (hemoglobin, hematocrit, red blood cell count, white blood cell count, white blood cell differential, and platelet count) will be obtained at screening, the first baseline visit (B1), entry, and all post-entry visits through week 24. CBCs will be obtained every two weeks during W24-34, and then every four weeks through the end of the study.

Chemistry

Serum sodium, potassium, chloride, bicarbonate, random glucose, blood urea nitrogen (BUN), creatinine, aspartate aminotransferase (AST/SGOT), alanine aminotransferase (ALT/SGPT), alkaline phosphatase, total bilirubin, and albumin will be obtained at screening, entry, and most post-entry visits, as detailed in Section 10. Note that total and direct bilirubin will be measured at screen and at all chemistry timepoints from Week 24 onwards.

Pregnancy Testing

A serum or urine β -human chorionic gonadotropin HCG test (urine test must have a sensitivity of 25 mIU/mL) will be obtained from female subjects with reproductive potential at screening and frequently

throughout the study (see Schedule of Events). Specifically, a serum or urine pregnancy test will be performed and reviewed on day of and prior to each study injection during stages 1-3 (DNA vaccines and MVA), prior to administering bNAbs (beginning of Stage 4), and every two weeks during lefitolimod administration (Stage 4), prior to second administration of bNAbs and the ATI (beginning of Stage 5) and every four weeks during the ATI (Stage 5). As of Protocol Version 2.2, no further lefitolimod will be administered.

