10.9 ART resumption phase (Stage 6)

Viral load criteria. Based on this rationale, we propose that treatment be initiated for any one of the following outcomes: (1) viremia > 50,000 copies RNA/mL for four weeks, (2) viremia > 10,000 copies RNA/mL for 6 weeks, (3) viremia > 2000 copies RNA/ml for 12 weeks or (4) viremia > 400 copies/RNA for 24 weeks. Operationally, this will allow for an acute viremic state that will need to resolve within 12 weeks, with high-level viremia only being allowed for a brief period. Post-treatment control (defined as viremia <400 copies RNA/mL) should be achieved prior to Week 24 post-virus rebound.

For any initial viral load greater than 400 copies/mL, we will bring individuals back immediately (within 3 working days or as soon as they are available) for a repeat test.

CD4+ T cell criteria. ART will also be reinitiated if the CD4+ T cell count declines to below 350 cells/μL on two consecutive visits. If an individual demonstrates a CD4+ T cell count <350 cells/uL, we will bring them back immediately (within 3 working days or as soon as they are available) for a repeat test.

Clinical criteria. ART will also be re-initiated for any symptoms suggestive of a severe acute retroviral syndrome, particularly signs of altered mental status or viral meningitis (severe headache, neck stiffness), but including unexplained rash, lymphadenopathy, and fevers. ART will also be re-initiated at the request of the study participant and/or her primary health care provider.

Post-ART monitoring. Once ART is reinitiated, subjects will be evaluated at Weeks 4 and 8 on ART. If viral load is not below the level of quantification by Week 8, participants will be evaluated every four weeks until the viral load is confirmed to less than the level of quantification. A follow up visit will occur 24 weeks after resumption of ART.

Routine safety studies, CD4+/CD8+ T cell counts and viral load will be performed at Weeks 4, 8, 24 and at any visits required between Week 8 and Week 24 to evaluate decrease of viral load to below level of quantification. Plasma and PBMCs will be collected and cryopreserved at the time of ART resumption and at Weeks 4, 8 and 24 on ART.

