10.10 End of study

Week 86: Subjects who receive study products through week 34 will be followed through 86. Should subjects initiate ART late in the follow-up phase, the last visit might be extended. Routine safety studies will be performed every four weeks during ART. CD4+/CD8+ T cell counts will be measured every four weeks. Plasma and PBMCs will be collected and cryopreserved at the end of the study.

Given the potential for delay immune-mediated adverse events, we will collect, analyze and report all data related to any medically attended adverse events (MAAEs), including potentially immune-mediated medical conditions (PIMMCs, Appendix A). All participants will be followed for 52 weeks after their last exposure to an experimental immunotherapy (Week 86, which is 53 weeks after the last dose lefitolimod and 52 weeks after the last dose of the bNAbs). Following the updates to Protocol Version 2.2 and the withholding of lefitolimod for some participants, Week 86 will no longer be 53 weeks following the last dose of lefitolimod for all enrolled participants.

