| ECG | | | | | | | | | | | | | | |
| PAXGene | 1 | | | | | | | | 1 | | | | | |
| PhenoSense Neutralizing Antibody Assay | | | | | | | | | | | | | | |
| Serum storage | 1 | | | | | | | | | | | | | |

Schedule of Events: Extended ATI (Week 48-86, Stage 5-Extended)

| | W48 | 49 | 50 | 51 | 52 | 53 | 54 | 55 | 56 | 57 | 58 | 60 | 62 | 64 | 66 | 68 | 70 | 72 | 74 | 76 | 78 | 80 | 82 | 84 | 86 or End Study ^Δ | ART re-initiation or Early Treatment Discontinuation |
|--|-----|----|----|----|----|----|----|----|----|----|----|----|----|----|----|----|----|----|----|----|----|----|----|----|------------------------------------|--|
| p24CE/IL-12 | | | | | | | | | | | | | | | | | | | | | | | | | | |
| p24CE&p55/IL-12 | | | | | | | | | | | | | | | | | | | | | | | | | | |
| MVA | | | | | | | | | | | | | | | | | | | | | | | | | | |
| Lefitolimod | | | | | | | | | | | | | | | | | | | | | | | | | | |
| bNAbs | | | | | | | | | | | | | | | | | | | | | | | | | | |
| ATI | 1 | 1 | 1 | 1 | 1 | 1 | 1 | 1 | 1 | 1 | 1 | 1 | 1 | 1 | 1 | 1 | 1 | 1 | 1 | 1 | 1 | 1 | 1 | 1 | 1 | 1 |
| Home Nurse Visit (Optional) | 1 | 1 | | 1 | 1 | 1 | 1 | 1 | 1 | 1 | 1 | 1 | 1 | 1 | 1 | 1 | 1 | 1 | 1 | 1 | 1 | 1 | 1 | 1 | 1 | 1 |
| Concomitant Medications | 1 | 1 | 1 | 1 | 1 | 1 | 1 | 1 | 1 | 1 | 1 | 1 | 1 | 1 | 1 | 1 | 1 | 1 | 1 | 1 | 1 | 1 | 1 | 1 | 1 | 1 |
| PE (symptom) | 1 | 1 | 1 | 1 | 1 | 1 | 1 | 1 | 1 | 1 | 1 | 1 | 1 | 1 | 1 | 1 | 1 | 1 | 1 | 1 | 1 | 1 | 1 | 1 | 1 | 1 |
| Clinical Assessment | 1 | 1 | 1 | 1 | 1 | 1 | 1 | 1 | 1 | 1 | 1 | 1 | 1 | 1 | 1 | 1 | 1 | 1 | 1 | 1 | 1 | 1 | 1 | 1 | 1 | 1 |
| Hematology/Chemistry | | | 1 | | | | 1 | | | | 1 | | 1 | | 1 | | 1 | | 1 | | 1 | | 1 | | 1 | 1 |
| T cell counts | 1 | | 1 | | 1 | | 1 | | 1 | | 1 | 1 | 1 | 1 | 1 | 1 | 1 | 1 | 1 | 1 | 1 | 1 | 1 | 1 | 1 | 1 |
| Plasma HIV RNA | 1 | 1 | 1 | 1 | 1 | 1 | 1 | 1 | 1 | 1 | 1 | 1 | 1 | 1 | 1 | 1 | 1 | 1 | 1 | 1 | 1 | 1 | 1 | 1 | 1 | 1 |
| Pregnancy testing | | | 1 | | | | 1 | | | | 1 | | 1 | | 1 | | 1 | | 1 | | 1 | | 1 | | 1 | 1 |
| bNAbs levels | 1 | | 1 | | 1 | | 1 | | 1 | | 1 | | | | | | | | | | | | | | | 1 |
| Cryopreservation plasma | 1 | | 1 | | 1 | | 1 | | 1 | | 1 | | 1 | | | | 1 | | | | 1 | | | | 1 | 1 |
| Cryopreservation PBMCs | | | 1 | | | | 1 | | | | 1 | | 1 | | | | 1 | | | | 1 | | | | 1 | 1 |
| LVBD | | | | | | | 1 | | | | | | | | | | | | | | | | | | 1 | 1 |
| Leukapheresis (optional) | | | | | | | | | | | | | | | | | | | | | | | | | | 1 |

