| LN FNA (optional) | | | | | | | | | | | | | | | | | | | | | | | | | | 1 |
| GALT (optional) | | | | | | | | | | | | | | | | | | | | | | | | | | 1 |
| Eye Exam | 1^ | 1^ | 1^ | | | | | | | | | | | | | | | | | | | | | | | 1* |
| ECG | | | | | | | | | | | | | | | | | | | | | | | | | | 1 |
| PAXGene | | | | | | | 1 | | | | | | | | | | | | | | | | | | | 1 |
| PhenoSense Neutralizing Antibody Assay | | | | | | | | | | | | | | | | | | | | | | | | | | 1 |
| Serum storage | | | | | | | | | | | 1 | | | | | | | | | | | | | | | 1 |

- Schedule of Events: Post ART Follow up (Weeks 4, 8 and 24 after ART initiation, Stage 6)
- Note: Visit windows are +/- 1 week for Stage 6

| Post ART-initiation: weeks 4, 8, and 24 on ART | W4-ART | W8-ART | W24-ART |
|--|--------|--------|---------|
| p24CE/IL-12 | | | |
| p24CE&p55/IL-12 | | | |
| MVA | | | |
| Lefitolimod | | | |
| bNAbs | | | |
| ATI | | | |
| Home Nurse Visit (Optional) | | | |
| Concomitant Medications | 1 | 1 | 1 |
| PE (symptom) | 1 | 1 | 1 |
| Clinical Assessment | 1 | 1 | 1 |
| Hematology/Chemistry | 1 | 1 | 1 |
| T cell counts | 1 | 1 | 1 |
| Plasma HIV RNA | 1 | 1 | 1 |
| Pregnancy testing | | | |
| bNAb levels | | | |
| Cryopreservation plasma | 1 | 1 | 1 |
| Cryopreservation PBMCs | 1 | 1 | 1 |
| LVBD | | | 1 |
| Leukapheresis (optional) | | | |
| LN FNA (optional) | | | |
| GALT (optional) | | | |
| Eye Exam | | | |
| ECG | | | |
| PAXGene | | | |
| PhenoSense Neutralizing Antibody Assay | | | |
| Serum storage | | | 1 |

^ indicates that eye exam may occur at any time point between week 46-50.

*Eye exam at early discontinuation visit is required only if the initial dose of bNAbs has been received and may be completed within 16 weeks of the bNAbs dose. This replaces the eye exam scheduled between Weeks 46-50. Only one follow-up eye exam is required assuming no other triggers for eye exam are warranted after Week 24.

Δ indicates the End Study visit will be 52 weeks after the last product administration. For participants who receive the final investigational product at Week 34, the End Study visit is Week 86. If participants discontinue treatment early, the End Study visit will be 52 weeks after the last IP is received. The window for the End Study visit will be +/- 2 weeks. The End Study visit does not equate to the final visit of the study.

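### Section 10.10 calls for safety labs and CD4/CD8 counts every four weeks on ART, but Section 10.9, the Stage 6 table and the 10.12 note schedule them only at Weeks 4, 8 and 24 once a participant is suppressed

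*Combined protocol and SAP*

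**What the plan says.** All the text below is in the current combined protocol and SAP.

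- **Section 10.10 (End of study):** "Routine safety studies will be performed every four weeks during ART. CD4+/CD8+ T cell counts will be measured every four weeks". No viral-load condition is attached. The section also provides for late restarts: "Should subjects initiate ART late in the follow-up phase, the last visit might be extended".
- **Section 9.5 (hematology):** "CBCs will be obtained every two weeks during W24-34, and then every four weeks through the end of the study". This covers CBCs only and makes no exception for participants back on ART.
- **Section 10.9 (Stage 6):** safety studies, CD4/CD8 counts and viral load at Weeks 4, 8 and 24 on ART. More visits are conditional: "If viral load is not below the level of quantification by Week 8, participants will be evaluated every four weeks", ending once suppression is confirmed. The same labs are drawn "and at any visits required between Week 8 and Week 24 to evaluate decrease of viral load to below level of quantification".
- **Section 10.12:** the Stage 6 table has three columns, for Weeks 4, 8 and 24 on ART, with hematology/chemistry and T-cell counts marked in each. The closing note lists the restart visit and then 4, 8 and 24 weeks later. Labs at restart come from the column headed "ART re-initiation or Early Treatment Discontinuation" in the extended ATI table, and labs at Week 86 from its End Study column. A footnote adds: "The End Study visit does not equate to the final visit of the study".

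**The concern.** Two frequencies stand for the same tests in the same participants, and the less frequent one is in the schedule that staff use to book visits. Following the table delivers less safety monitoring than Section 10.10 asks for.

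The participants affected are those suppressed by Week 8 on ART, because the extra visits in Section 10.9 depend on viral load alone. ART can also be restarted because CD4 falls below 350 on two consecutive visits. Such a participant, once suppressed, could go 16 weeks without a scheduled study CD4 count.

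Liver monitoring makes the frequency matter more. Version 2.2 followed a Grade 4 ALT elevation, and its change log describes liver events possibly related to lefitolimod and/or the bNAbs. Appendix E sets an LFT schedule for all participants that ends in monthly tests. Section 10.8 repeats it under the ATI period. Neither place says whether it continues once ART restarts, and the Stage 6 table has no monthly chemistry after Week 8.

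**Working it through.** The plan gives no figure to reproduce, so this is a comparison of texts and a count of visits.

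**Inputs.** Four-weekly rule: Section 10.10. Table rule: Weeks 4, 8 and 24 on ART (Section 10.9, Stage 6 table, 10.12 note) plus the Week 86 End Study visit. The restart-visit draw is common to both and is not counted. The participant is suppressed by Week 8 on ART. Restart weeks are illustrative assumptions.

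**First 24 weeks on ART, restarts up to Week 62.**
- Four-weekly rule: 4, 8, 12, 16, 20, 24 = 6 draws.
- Table: 4, 8, 24 = 3 draws. Missing: 12, 16 and 20.
- Longest gap: 24 − 8 = 16 weeks. Stage 6 visit windows are ±1 week, so it can reach 25 − 7 = 18.

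**Through Week 86.** For restart at week r, the four-weekly rule gives (86 − r)/4 draws. The table gives r+4, r+8, r+24 (if no later than 86) and 86.

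| Restart week | Four-weekly | Table | Longest gap under table (weeks) |
|---|---|---|---|
| 38 | 12 | 4 (42, 46, 62, 86) | 24 |
| 46 | 10 | 4 (50, 54, 70, 86) | 16 |
| 54 | 8 | 4 (58, 62, 78, 86) | 16 |
| 62 | 6 | 3 (66, 70, 86) | 16 |
| 66 | 5 | 3 (70, 74, 86) | 12 |
| 70 | 4 | 3 (74, 78, 86) | 8 |
| 74 | 3 | 3 (78, 82, 86) | 4 |

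After Week 62 the effect shrinks, because Week 86 falls inside the gap.

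**If the last visit is extended to Week 24 on ART.**
- Restarts at Weeks 66, 70 and 74: 6 draws against 4, with gaps of 12, 8 and 12 weeks.
- Restarts at Weeks 78, 82 and 86: 6 against 3, with a 16-week gap.
- Latest date: 86 + 24 = Week 110, inside the 112-week maximum in the synopsis.

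**If viral load is still quantifiable at Week 8,** the conditional visits in Section 10.9 close part or all of the gap.

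**Could ART in Section 10.10 be a slip for ATI?** That would not remove the conflict. Section 10.8 requires CD4/CD8 counts every two weeks in the ATI, so a four-weekly count would contradict it. The preceding sentence in 10.10 also concerns subjects who start ART.

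**The case against.** The strongest reply is that Section 10.10 is the outlier. Section 10.9, the Stage 6 table and the 10.12 note agree with one another. Section 10.9 also states when four-weekly visits apply, and that condition would do little for labs that were four-weekly anyway. The change log for Version 1.9 shows the Week 4, 8 and 24 schedule being specified deliberately. The Version 1.4 log records that extended-ATI CD4 checks were once four-weekly, so the 10.10 sentences may be leftover text. Section 9.5 is weak support for a separate rule, since the Version 1.9 log says its CBC wording was updated to reflect the schedule of events.

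This is plausible and bears on which fix is right. It does not settle the matter, because the sentences remain in force and nothing in the current text withdraws them.

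Four stronger readings that a reader might infer are not supported:

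- *The two rules are mutually impossible.* They are not. Nothing in 10.9 or 10.12 forbids extra draws, and a four-weekly schedule satisfies every text. The defect is that the schedule omits draws Section 10.10 requires.
- *Liver tests stop on ART.* Chemistry is drawn at restart and at Weeks 4, 8 and 24. The issue is frequency.
- *Appendix E already mandates monthly LFTs on ART.* Its reference to all participants points that way, but the bullet sits among Stage 5 entry rules and Section 10.8 places it under the ATI. The text is unclear.
- *The SMC loses oversight.* It meets every 3 months (about 13 weeks), so a 16-week gap could leave one review without a new routine value from one participant. Adverse-event review, event-triggered SMC reviews and the weekly PSRT review continue.

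**Conclusion.** The inconsistency is real and lies in the current text. For a participant suppressed by Week 8 on ART, following the table gives 3 draws instead of 6 over 24 weeks, with a nominal 16-week gap in chemistry and CD4/CD8 counts. Through Week 86 the shortfall ranges from 8 draws with a 24-week gap (restart at Week 38) to none (restart at Week 74). These counts assume that staff book only the visits in the table and that nobody reconciles it with Section 10.10. The documents do not show which frequency the sponsor intends.

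This is an internal inconsistency in safety monitoring. It should be corrected because it changes what is done for participants. No endpoint, power or sample-size figure depends on it.

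**What to change.** Choose one rule and state it everywhere.

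1. **Keep the four-weekly rule.** Add hematology/chemistry and T-cell counts every four weeks on ART to Section 10.9, the Stage 6 table and the 10.12 note, through Week 86 or the extended last visit. The cost is routine draws that 10.10 already calls for. Through Week 86 that means 8 extra for a restart at Week 38, 6 at Week 46, 3 at Week 62, 1 at Week 70 and none at Week 74. With follow-up extended to Week 24 on ART, it means 2 or 3 extra for restarts from Week 66.
2. **Keep Weeks 4, 8 and 24,** if the sponsor and SMC confirm that this is intended. Delete the two 10.10 sentences and limit the Section 9.5 CBC clause to time off ART. The cost is a text edit, and the 16-week gap is then a stated choice.

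In either case, add one sentence to Section 10.8 and Appendix E saying whether the monthly LFTs continue after ART restart, and make the Stage 6 table match.

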10.11 Premature discontinuation

Routine safety studies will be performed. Plasma HIV RNA levels and CD4+/CD8+ T cell counts will be measured. Plasma and PBMCs will be collected and cryopreserved and any other specimen collection deemed pertinent to safety or data integrity as assessed by PI/Co-I.

Participants who discontinue prematurely will have an end of study visit scheduled 52 weeks after the last dose of study product administration. This will include routine safety studies, CD4+/CD8+ T cell counts, plasma and PBMCs cryopreservation, and any other specimen collection deemed pertinent to safety or data integrity as assessed by PI/Co-I.

10.12 Schedule of events

Schedule of Events: DNA/MVA Vaccine (Screen to Week 22, Stages 1-3)

Note: Visit windows are +/- 1 week for vaccines during Stage 1-3

| DNA/MVA Vaccine (Screen Week to 22, Stages 1-3) | S | B1 | B2 D0 | Wk 1 | W4 | W12 | W20 | W22 |
|---|----|----|----------|------|----|-----|-----|-----|
| p24CE/IL-12 | | | 1 | | 1 | | | |
| p24CE&p55/IL-12 | | | | | | 1 | | |
| MVA | | | | | | | 1 | |
| Lefitolimod | | | | | | | | |
| bNAbs | | | | | | | | |
| ATI | | | | | | | | |
| Home Nurse Visit (Optional) | | | | | | | | |
| Concomitant Medications | 1 | 1 | 1 | | 1 | 1 | 1 | 1 |
| PE (symptom) | 1 | 1 | 1 | | 1 | 1 | 1 | 1 |
| Clinical Assessment | 1 | 1 | 1 | | 1 | 1 | 1 | 1 |
| Hematology/Chemistry | 1 | 1 | 1 | 1 | 1 | 1 | 1 | 1 |
| T cell counts | 1 | 1 | 1 | 1 | 1 | 1 | 1 | 1 |
| Plasma HIV RNA | 1 | 1 | 1 | 1 | 1 | 1 | 1 | 1 |
| Pregnancy testing | 1 | | 1 | | 1 | 1 | 1 | |
| bNAb levels | | | | | | | | |
| Cryopreservation plasma | | 1 | 1 | 1 | | 1 | 1 | 1 |
| Cryopreservation PBMCs | | 1 | 1 | 1 | | 1 | 1 | 1 |
| LVBD | | 1 | 1 | | | | 1 | 1 |
| Leukapheresis (optional) | | 1* | | | | | | |
| LN FNA (optional) | | 1* | | | | | | 1 |
| GALT (optional) | | 1* | | | | | | 1 |
| Eye Exam | 1# | | | | | | | |
| ECG | 1 | | | | | | | |
| PAXGene | | | 1 | 1 | | | | 1 |
| PhenoSense Neutralizing Antibody Assay | 1 | | | | | | | |
| Serum storage | | 1^ | | | | | | |

*Optional baseline studies may be performed at any visit after screen through B2D0. #Eye exam may be done at any visit from S prior to B2D0. ^Serum can be stored at any visit within 4 weeks of or on B2D0

Schedule of Events: bNAb/TLR9 (Week 24-33, Stage 4)

Note: Visit windows are +/- 1 week for bNAbs. Week 25 lefitolimod window is 7 days and +/- 3 days after the bNAbs. Following the initial dose of lefitolimod, weekly doses may be administered on any day of the week provided the doses are at least 5 days apart.

| | W24 | W25 | W26 | W27 | W28 | W29 | W30 | W31 | W32 | W33 | |
|--|-----|-----|-----|-----|-----|-----|-----|-----|-----|-----|--|
| p24CE/IL-12 | | | | | | | | | | | |
| p24CE&p55/IL-12 | | | | | | | | | | | |
| MVA | | | | | | | | | | | |
| Lefitolimod | | 1 | 1 | 1 | 1 | 1 | 1 | 1 | 1 | 1 | Note: No more lefitolimod will be administered as of V2.2. |
| bNAbs | 1 | | | | | | | | | | |
| ATI | | | | | | | | | | | |
| Home Nurse Visit (Optional) | | | | | | | | | | | |
| Concomitant Medications | 1 | 1 | 1 | 1 | 1 | 1 | 1 | 1 | 1 | 1 | |
| PE (symptom) | 1 | 1 | 1 | 1 | 1 | 1 | 1 | 1 | 1 | 1 | |
| Clinical Assessment | 1 | 1 | 1 | 1 | 1 | 1 | 1 | 1 | 1 | 1 | |
| Hematology/Chemistry | 1 | | 1 | | 1 | | 1 | | 1 | | |
| T cell counts | 1 | | | | 1 | | 1 | | 1 | | |
| Plasma HIV RNA | 1 | | | | 1 | | 1 | | 1 | | |
| Pregnancy testing | 1 | | 1 | | 1 | | 1 | | 1 | | |
| bNAb levels | | | 1 | | 1 | | 1 | | 1 | | |
| Cryopreservation plasma | 1 | | 1 | | 1 | | 1 | | 1 | | |
| Cryopreservation PBMCs | 1 | | | | 1 | | | | 1 | | |
| LVBD | 1 | | | | | | | | | | |
| Leukapheresis (optional) | | | | | | | | | | | |
| LN FNA (optional) | | | | | | | | | | | |
| GALT (optional) | | | | | | | | | | | |
| Eye Exam | | | | | | | | | | | |
| ECG | | | | | | | | | | | |
| PAXGene | 1 | | | | | | | | | | |
| PhenoSense Neutralizing Antibody Assay | | | | | | | | | | | |
| Serum storage | 1 | | | | | | | | | | |

bNAb Levels

Schedule of Events: bNAb/ATI (Week 34-47, Stage 5)

Note: Visit window is +/- 1 week for bNAbs during stage 5

| | W34 | W35 | W36 | W37 | W38 | W39 | W40 | W41 | W42 | W43 | W44 | W45 | W46 | W47 |
|--|-----|-----|-----|-----|-----|-----|-----|-----|-----|-----|-----|-----|-----|-----|
| p24CE/IL-12 | | | | | | | | | | | | | | |
| p24CE&p55/IL-12 | | | | | | | | | | | | | | |
| MVA | | | | | | | | | | | | | | |
| Lefitolimod | | | | | | | | | | | | | | |
| bNAbs | 1 | | | | | | | | | | | | | |
| ATI | 1 | 1 | 1 | 1 | 1 | 1 | 1 | 1 | 1 | 1 | 1 | 1 | 1 | 1 |
| Home Nurse Visit (Optional) | | 1 | 1 | 1 | 1 | 1 | 1 | 1 | 1 | 1 | 1 | 1 | 1 | 1 |
| Concomitant Medications | 1 | 1 | 1 | 1 | 1 | 1 | 1 | 1 | 1 | 1 | 1 | 1 | 1 | 1 |
| PE (symptom) | 1 | 1 | 1 | 1 | 1 | 1 | 1 | 1 | 1 | 1 | 1 | 1 | 1 | 1 |
| Clinical Assessment | 1 | 1 | 1 | 1 | 1 | 1 | 1 | 1 | 1 | 1 | 1 | 1 | 1 | 1 |
| Hematology/Chemistry | 1 | 1 | 1 | 1 | 1 | | 1 | | 1 | | | | 1 | |
| T cell counts | 1 | | 1 | | 1 | | 1 | | 1 | | 1 | | 1 | |
| Plasma HIV RNA | 1 | 1 | 1 | 1 | 1 | 1 | 1 | 1 | 1 | 1 | 1 | 1 | 1 | 1 |
| Pregnancy testing | 1 | | | | 1 | | | | 1 | | | | 1 | |
| bNAb levels | 1 | | 1 | | 1 | | 1 | | 1 | | 1 | | 1 | |
| Cryopreservation plasma | 1 | | 1 | | 1 | | 1 | | 1 | | 1 | | 1 | |
| Cryopreservation PBMCs | 1 | | | | 1 | | | | 1 | | | | 1 | |
| LVBD | 1 | | | | | | | | 1 | | | | | |
| Leukapheresis (optional) | 1 | | | | | | | | | | | | | |
| LN FNA (optional) | 1 | | | | | | | | | | | | | |
| GALT (optional) | 1 | | | | | | | | | | | | | |
| Eye Exam | | | | | | | | | | | | | 1^ | 1^ |
| ECG | | | | | | | | | | | | | | |
| PAXGene | 1 | | | | | | | | 1 | | | | | |
| PhenoSense Neutralizing Antibody Assay | | | | | | | | | | | | | | |
| Serum storage | 1 | | | | | | | | | | | | | |

Schedule of Events: Extended ATI (Week 48-86, Stage 5-Extended)

| | W48 | 49 | 50 | 51 | 52 | 53 | 54 | 55 | 56 | 57 | 58 | 60 | 62 | 64 | 66 | 68 | 70 | 72 | 74 | 76 | 78 | 80 | 82 | 84 | 86 or End Study ^Δ | ART re-initiation or Early Treatment Discontinuation |
|--|-----|----|----|----|----|----|----|----|----|----|----|----|----|----|----|----|----|----|----|----|----|----|----|----|------------------------------------|--|
| p24CE/IL-12 | | | | | | | | | | | | | | | | | | | | | | | | | | |
| p24CE&p55/IL-12 | | | | | | | | | | | | | | | | | | | | | | | | | | |
| MVA | | | | | | | | | | | | | | | | | | | | | | | | | | |
| Lefitolimod | | | | | | | | | | | | | | | | | | | | | | | | | | |
| bNAbs | | | | | | | | | | | | | | | | | | | | | | | | | | |
| ATI | 1 | 1 | 1 | 1 | 1 | 1 | 1 | 1 | 1 | 1 | 1 | 1 | 1 | 1 | 1 | 1 | 1 | 1 | 1 | 1 | 1 | 1 | 1 | 1 | 1 | 1 |
| Home Nurse Visit (Optional) | 1 | 1 | | 1 | 1 | 1 | 1 | 1 | 1 | 1 | 1 | 1 | 1 | 1 | 1 | 1 | 1 | 1 | 1 | 1 | 1 | 1 | 1 | 1 | 1 | 1 |
| Concomitant Medications | 1 | 1 | 1 | 1 | 1 | 1 | 1 | 1 | 1 | 1 | 1 | 1 | 1 | 1 | 1 | 1 | 1 | 1 | 1 | 1 | 1 | 1 | 1 | 1 | 1 | 1 |
| PE (symptom) | 1 | 1 | 1 | 1 | 1 | 1 | 1 | 1 | 1 | 1 | 1 | 1 | 1 | 1 | 1 | 1 | 1 | 1 | 1 | 1 | 1 | 1 | 1 | 1 | 1 | 1 |
| Clinical Assessment | 1 | 1 | 1 | 1 | 1 | 1 | 1 | 1 | 1 | 1 | 1 | 1 | 1 | 1 | 1 | 1 | 1 | 1 | 1 | 1 | 1 | 1 | 1 | 1 | 1 | 1 |
| Hematology/Chemistry | | | 1 | | | | 1 | | | | 1 | | 1 | | 1 | | 1 | | 1 | | 1 | | 1 | | 1 | 1 |
| T cell counts | 1 | | 1 | | 1 | | 1 | | 1 | | 1 | 1 | 1 | 1 | 1 | 1 | 1 | 1 | 1 | 1 | 1 | 1 | 1 | 1 | 1 | 1 |
| Plasma HIV RNA | 1 | 1 | 1 | 1 | 1 | 1 | 1 | 1 | 1 | 1 | 1 | 1 | 1 | 1 | 1 | 1 | 1 | 1 | 1 | 1 | 1 | 1 | 1 | 1 | 1 | 1 |
| Pregnancy testing | | | 1 | | | | 1 | | | | 1 | | 1 | | 1 | | 1 | | 1 | | 1 | | 1 | | 1 | 1 |
| bNAbs levels | 1 | | 1 | | 1 | | 1 | | 1 | | 1 | | | | | | | | | | | | | | | 1 |
| Cryopreservation plasma | 1 | | 1 | | 1 | | 1 | | 1 | | 1 | | 1 | | | | 1 | | | | 1 | | | | 1 | 1 |
| Cryopreservation PBMCs | | | 1 | | | | 1 | | | | 1 | | 1 | | | | 1 | | | | 1 | | | | 1 | 1 |
| LVBD | | | | | | | 1 | | | | | | | | | | | | | | | | | | 1 | 1 |
| Leukapheresis (optional) | | | | | | | | | | | | | | | | | | | | | | | | | | 1 |
| LN FNA (optional) | | | | | | | | | | | | | | | | | | | | | | | | | | 1 |
| GALT (optional) | | | | | | | | | | | | | | | | | | | | | | | | | | 1 |
| Eye Exam | 1^ | 1^ | 1^ | | | | | | | | | | | | | | | | | | | | | | | 1* |
| ECG | | | | | | | | | | | | | | | | | | | | | | | | | | 1 |
| PAXGene | | | | | | | 1 | | | | | | | | | | | | | | | | | | | 1 |
| PhenoSense Neutralizing Antibody Assay | | | | | | | | | | | | | | | | | | | | | | | | | | 1 |
| Serum storage | | | | | | | | | | | 1 | | | | | | | | | | | | | | | 1 |

- Schedule of Events: Post ART Follow up (Weeks 4, 8 and 24 after ART initiation, Stage 6)
- Note: Visit windows are +/- 1 week for Stage 6

| Post ART-initiation: weeks 4, 8, and 24 on ART | W4-ART | W8-ART | W24-ART |
|--|--------|--------|---------|
| p24CE/IL-12 | | | |
| p24CE&p55/IL-12 | | | |
| MVA | | | |
| Lefitolimod | | | |
| bNAbs | | | |
| ATI | | | |
| Home Nurse Visit (Optional) | | | |
| Concomitant Medications | 1 | 1 | 1 |
| PE (symptom) | 1 | 1 | 1 |
| Clinical Assessment | 1 | 1 | 1 |
| Hematology/Chemistry | 1 | 1 | 1 |
| T cell counts | 1 | 1 | 1 |
| Plasma HIV RNA | 1 | 1 | 1 |
| Pregnancy testing | | | |
| bNAb levels | | | |
| Cryopreservation plasma | 1 | 1 | 1 |
| Cryopreservation PBMCs | 1 | 1 | 1 |
| LVBD | | | 1 |
| Leukapheresis (optional) | | | |
| LN FNA (optional) | | | |
| GALT (optional) | | | |
| Eye Exam | | | |
| ECG | | | |
| PAXGene | | | |
| PhenoSense Neutralizing Antibody Assay | | | |
| Serum storage | | | 1 |

^ indicates that eye exam may occur at any time point between week 46-50.

*Eye exam at early discontinuation visit is required only if the initial dose of bNAbs has been received and may be completed within 16 weeks of the bNAbs dose. This replaces the eye exam scheduled between Weeks 46-50. Only one follow-up eye exam is required assuming no other triggers for eye exam are warranted after Week 24.

Δ indicates the End Study visit will be 52 weeks after the last product administration. For participants who receive the final investigational product at Week 34, the End Study visit is Week 86. If participants discontinue treatment early, the End Study visit will be 52 weeks after the last IP is received. The window for the End Study visit will be +/- 2 weeks. The End Study visit does not equate to the final visit of the study.

The schedule during the ATI period will be defined by clinical course and the characteristics of any virus rebound. ART will be initiated for clinical events, sustained drop in CD4+T cell counts or sustained increased in viremia. Prior to these events, subjects will be followed weekly for 24 weeks and then every two weeks. Once ART is initiated, subjects will be followed at the time of ART restart, and at 4, 8, and 24 weeks after restart.

Note: In cases in which clinical laboratory testing is performed remotely (for example, if trying to minimize in-person visits during the ATI for individuals living outside of San Francisco during the SARS-CoV-2 pandemic), storage of specimens may be deferred when samples are not collected on site.

